2.6.3 Procedures for LDF examination and moxibustion intervention

A four-channel LDF (PeriFlux System 5000, Sweden) will be used to measure the microcirculatory characteristics of meridian phenomena for the Heart and Lung meridians, which could monitor 4 measuring sites simultaneously. The participants will be asked to stabilize for 15 minutes in a supine position in the experimental room before formal examination. They will be informed to keep silent and normal breath and avoid limb movement during the whole measuring period. The probes will be left at relevant measuring sites. Blood flow curve will be recorded constantly using Perisoft software (PeriFlux, Sweden). Perfusion units (PU) of microcirculatory flux in the measuring sites will be calculated by the software [PU = concentration of moving blood cells (CMBC) × velocity (V)].

(1) Healthy control group and COPD group

The probes will be left at 4 measuring acupoints, which include Shenmen (HT7) and Shaohai (HT3) of the Heart meridian, Taiyuan (LU9) and Chize (LU5) of the Lung meridian. The blood flow curve and PU will be recorded for 5 minutes.

(2) Healthy intervention group

Two sessions of moxibustion intervention will be performed in the Heart meridian and Lung meridian successively. The washout period between the two sessions is at least one day.

1) Intervention in the Heart meridian: By igniting the moxa stick and inserting it into a homemade moxibustion holder to adjust the appropriate angle and height, moxibustion will be performed above Shaohai (HT3) of Heart meridian for 15 minutes. During moxibustion, the probes will detect the blood flow curve and PU in four sites in two meridians, which include Shaohai (HT3) of the Heart meridian, the midpoint of the Heart meridian along the left forearm (i.e. the midpoint of the line

between HT3 and HT7), Chize (LU5) of the Lung meridian, and the midpoint of the Lung meridian along the left forearm(i.e. the midpoint of the line between LU5 and LU9). The measuring time points include 5 minutes before moxibustion, 15 minutes during moxibustion and 5 minutes after stopping moxibustion.

2)Intervention in the Lung meridian: The moxibustion acupoint is Chize (LU5) of the Lung meridian. The LDF examination, moxibustion procedure, measuring sites and time points are the same as 1).

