2.6.4 Concomitant treatments

During the study period, all the participants in the COPD group will maintain their previous treatment regimen. If additional medications or other treatments are used during the study period due to any reasons, the details (e.g. the name, administration time and dosage of the medication) should be documented.

Besides, participants in the healthy control group and healthy intervention group should not take any medications during the full study period. If drugs or other treatments are adopted due to sudden diseases, relevant information should be documented and researchers will evaluate whether they should be withdrawn from the study.

3. Outcome measurement

Primary outcomes will be blood flow curve and blood perfusion units (PU) of relevant sites along the Heart and Lung meridians.

4. Safety evaluation

Adverse events (AEs) that occur during the trial will be recorded and assessed by the investigators during each examination session and at each visit next time. If serious AEs occur, the researchers should report them to the principal investigator and ethics committee immediately, who will make a decision on whether the participant should be withdrawn from the study.

5. Ethical approval and study registration

Ethics approval (approval document No: ZCMU-KY-2019-042, April 29, 2019) was obtained from the Ethics Committee of Zhejiang Chinese Medical University. The purpose, contents and potential risks of the research will be fully explained to the

participants and their families. All participants will complete the informed consent form before participating in the study. All participants' personal and disease information will be kept confidential.

6. Quality control

(1) The trial protocol has been modified according to suggestions from experienced acupuncturists.

(2) Before the trial, all researchers who enroll participants and collect data must attend a series of training sessions. These training sessions will ensure that all research staff involved fully understand the trial protocol and standard operating procedures (SOP).

[figure not shown]
(3) SOP of the examination method is designed before the trial.

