2.3 Statistical analysis

All data in this study will be analyzed by a blinded statistician. Independent sample T test and Chi-square test (χ^2 test) will be used for numerical variables and categorical variables, respectively. When the distribution of variables is abnormal, a non-parametric test will be selected. A P value < 0.05 will be considered statistically significance.

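### The pre-moxibustion PU recorded in each session has no stated role in the SAP, so a comparison between the Heart and Lung sessions may lose precision by an amount the plan does not let us fix

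*Combined protocol and SAP*

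**What the plan says.** Protocol Part 2, section 2.6.3 (2), describes the healthy intervention group: "Two sessions of moxibustion intervention will be performed in the Heart meridian and Lung meridian successively". On spacing it says "The washout period between the two sessions is at least one day". In the Heart session, "the probes will detect the blood flow curve and PU in four sites in two meridians": HT3, the Heart midpoint of the left forearm, LU5 and the Lung midpoint. On timing, "The measuring time points include 5 minutes before moxibustion, 15 minutes during moxibustion and 5 minutes after stopping moxibustion". For the Lung session, "The LDF examination, moxibustion procedure, measuring sites and time points are the same as 1". Every participant in this group should therefore have two pre-moxibustion recordings at each of four sites, one per session.

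Part 2, section 3, defines the outcome: "Primary outcomes will be blood flow curve and blood perfusion units (PU) of relevant sites along the Heart and Lung meridians". It does not mention change from baseline.

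Part 3, section 2.3, gives the whole inferential plan. Numerical and categorical variables get "Independent sample T test and Chi-square test" respectively, and "When the distribution of variables is abnormal, a non-parametric test will be selected". It names no covariate, change score, paired test, ANCOVA or mixed model. It also does not say which contrast the tests serve in this group.

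**The concern.** One of the two study aims is the surface-surface association between the two meridians. A natural way to examine it is to ask whether PU at a given site differs according to which meridian is heated, which is a comparison between sessions.

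The sessions are at least one day apart, so PU at a site can start from a different level in each. Re-placement of the probes is a likely reason, although the plan does not state it. Any other day-to-day change in skin blood flow would act in the same way.

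Pairing the sessions within a person removes that person's stable level but not this session-specific shift. The session's own pre-moxibustion PU carries information about the shift, and the trial already collects it. Leaving it out costs precision in a group of 40 whose size was set without a power calculation (Part 2, section 2.2).

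**Working it through.** **Inputs.** From the documents: 40 participants in the group (Part 2, section 2.1), both sessions in the same people, a pre-moxibustion recording in each (section 2.6.3), and a 0.05 significance threshold (SAP 2.3). The plan does not state sidedness, and two-sided is assumed. It gives no effect size, SD, correlation or power, so it has no figure of its own to reproduce. Everything below on size is an assumption shown over a range.

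**Step 1: variance.** For one person and one site, let D be the PU difference between sessions during moxibustion, and B the same difference before moxibustion. Let rho be the correlation of D and B. Regressing D on B multiplies the residual variance by 1 − rho². The intercept estimates the session difference at equal baselines.

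**Step 2: power.** A paired t test with n = 40 and 39 df has 80% power at a standardised difference d = 0.454 (noncentrality 0.454 × √40 = 2.87). After adjustment, d becomes 0.454/√(1 − rho²) with 38 df.

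| rho | 1 − rho² | adjusted d | power (%) | power with allowance, step 3 (%) |
|---|---|---|---|---|
| 0.1 | 0.99 | 0.457 | 80.3 | 79.3 |
| 0.2 | 0.96 | 0.464 | 81.5 | 80.5 |
| 0.3 | 0.91 | 0.476 | 83.5 | 82.5 |
| 0.5 | 0.75 | 0.525 | 89.8 | 89.1 |
| 0.7 | 0.51 | 0.636 | 97.5 | 97.2 |

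**Step 3: a small allowance.** The fourth column charges only the lost degree of freedom. The intercept's variance also grows when the mean of B is not zero by chance. With normal data the average factor is 1 + 1/(n − 3) = 1 + 1/37 = 1.027. The last column uses d = 0.454/√[1.027 × (1 − rho²)]. Adjustment breaks even when (1 − rho²) × 38/37 = 1, which is rho = √(1/38), about 0.16. At rho = 0 it costs about one power point.

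**Step 4: simulation.** PU was modelled as person + session + error with total variance 1, 40 people, a true difference of 0.4 and 4,000 runs. Here rho = session variance/(session + error variance).

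| person / session / error variance | rho | independent t | paired t | paired, change score | paired + baseline difference |
|---|---|---|---|---|---|
| 0.3 / 0.5 / 0.2 | 0.71 | 0.40 | 0.54 | 0.80 | 0.84 |
| 0.5 / 0.3 / 0.2 | 0.60 | 0.39 | 0.69 | 0.79 | 0.86 |
| 0.5 / 0.1 / 0.4 | 0.20 | 0.42 | 0.71 | 0.51 | 0.71 |
| 0.5 / 0 / 0.5 | 0 | 0.40 | 0.70 | 0.42 | 0.68 |

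With no true difference, the adjusted analysis rejected in 4.3% to 5.4% of runs. The independent t test on raw PU rejected in about 0.5% to 2%, because it ignores the pairing.

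**Step 5: a systematic session shift.** Suppose the second session runs 0.5 higher both before and during moxibustion, with no true effect (variances 0.5 / 0.2 / 0.3, so rho = 0.2/0.5 = 0.4). Raw PU is biased by 0.50. The regression removes only its slope's share, leaving 0.50 × (1 − 0.4) = 0.30. The change score leaves 0. Simulation gave the same three values.

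**The case against.** The strongest reply is that SAP 2.3 does not say which contrast its test serves. If the comparison is before versus during moxibustion, the pre-moxibustion PU is the comparator and is in use. The SAP also does not say whether PU or change in PU is tested. This stands: the documents do not show that the baseline is discarded, only that no role is stated for it. The point is therefore conditional on a between-session comparison.

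A second reply is that the power figures start from a paired test, whereas the plan names an independent-sample test. This also stands. The figures measure what adjustment adds once pairing is in place, and where session variance is small, pairing supplies nearly all the gain.

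A third reply is that rho may be low once the stable person level has been removed. Nothing in the documents excludes that.

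A reader might also infer that chance differences in starting level produce false meridian differences. They can distort a single estimate, but random variation does not raise type I error, and the planned independent test is conservative here. A systematic shift between sessions is a different matter and could bias the comparison. Section 2.6.3 describes the sessions as Heart then Lung and mentions no randomised order.

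**Conclusion.** The point holds as one of efficiency, limited to a between-session comparison in the healthy intervention group. For that comparison SAP 2.3 names no method that uses the baseline, and a better one is available from data already collected.

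The size is unknown. Relative to an 80% paired test, the gain runs from nothing useful at rho of 0.1 to 0.2, through about 10 points at 0.5, to about 17 points at 0.7. Below about 0.16, adjustment costs up to about one point. These figures assume n = 40 with complete data, two-sided 5% testing and normal differences.

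Two stronger readings are not supported. The documents do not establish that substantial power is lost, because they give nothing that fixes rho. Nor do they state that probes are re-placed, which is inferred from the gap between sessions. The COPD versus healthy control comparison rests on a single 5-minute recording per person with no earlier baseline, so it is unaffected.

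**What to change.** In SAP 2.3, state for the healthy intervention group that the between-session comparison is made within person. At each site, regress the between-session difference in PU (during moxibustion, and separately after it) on the between-session difference in pre-moxibustion PU at that site, and test the intercept. The difference-on-difference form should be named explicitly. A mixed model with raw session baselines and a random person effect is not generally equivalent, because it blends within-person and between-person slopes.

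Because session order reads as fixed, also report the between-session difference in change from the session's own baseline as a sensitivity analysis. The regression only partly removes a systematic session shift, whereas the change score removes one that acts equally before and during moxibustion. The change score should not replace the regression: it reduces variance relative to raw PU only when rho exceeds SD(B)/(2 × SD(D)), which is 0.5 if the SDs are equal.

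The non-parametric fallback should be given a within-person form too, for example a signed-rank test on that change-score difference.

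The cost is a few lines in SAP 2.3, one residual degree of freedom, up to about one power point if rho is near zero, and one extra analysis. No new data or participants are needed, and SPSS v20 can fit the regression.

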ID: 2019ZY004-MERIDIAN

Research title:

A study on the microcirculatory characteristics of meridian phenomenon for the heart and lung meridians based on patients with chronic obstructive pulmonary disease

Date: March 25, 2019

Study Protocol

Part1. Study introduction and objectives

(1) Brief introduction

This study will include 40 patients with chronic obstructive pulmonary disease (COPD), and 80 healthy volunteers. Laser doppler examination will be adopted to assess the microcirculatory characteristics of meridian phenomena and investigate the site specificity for the meridian-visceral association and surface-surface association between two specific meridians.

(2) Study objects

1) This study aims to detect the microcirculatory characteristics of meridian phenomena using laser doppler flowmetry(LDF). Thus, the biological characteristics of meridian phenomenon could be presented objectively in a scientific methodology.

2) This study aims to investigate the site specificity for the meridian-visceral association and surface-surface association between two specific meridians.

Part2. Study program

1.Study subjects

The subjects of this study include two kinds of participants, which includes healthy volunteers and patients with COPD.

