1.1 Data entry

(1) The original data collection

All observation scales will be measured on a "one to one" basis according to the unified standard, and the subject will be completed independently under the guidance of the investigators to ensure complete and correct completion. In the spot, check whether the filling quantity is accurate. If any omission or blurring is found in the case report forms, the assessors should verify the original data in time.

(2) Data entry and statistics

The Excel spreadsheet is used to record the original data and ensure it is accurate and reliable. A blinded statistician is employed to carry out the statistical analysis and the research managers should verify whether the statistical methods are appropriate.

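### SAP 2.3 fixes neither the analysis scale for PU nor a between-site contrast; if sites are compared on raw PU, a uniform proportional COPD effect can look site-specific

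*Combined protocol and SAP*

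**What the plan says.** - **Objective.** Part 1, Study objects: "This study aims to investigate the site specificity for the meridian-visceral association and surface-surface association between two specific meridians".
- **Outcome.** Part 2, section 3: "Primary outcomes will be blood flow curve and blood perfusion units (PU) of relevant sites along the Heart and Lung meridians". Section 2.6.3 defines PU as the product of the concentration of moving blood cells and their velocity. In the healthy control and COPD groups it is recorded for 5 minutes at HT7, HT3, LU9 and LU5. In the healthy intervention group it is recorded before, during and after moxibustion, at two Heart and two Lung sites.
- **Test.** Part 3, section 2.3: "Independent sample T test and Chi-square test (χ^2 test) will be used for numerical variables and categorical variables, respectively". No transformation is mentioned.
- **Fallback.** The same section: "When the distribution of variables is abnormal, a non-parametric test will be selected". The test is not named, and nothing says how abnormality is judged.
- **Summary statistics.** Part 3, section 2.2 lists mean, SD, median, range and quartiles, but no geometric mean, ratio or confidence interval.
- **Who decides.** The statistician is blinded (Part 2, section 2.5, where the blinding extends to the protocol itself). Part 3, section 1.1 adds that "the research managers should verify whether the statistical methods are appropriate", with no time given for that check.

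**The concern.** Site specificity is a claim about a difference between sites: that COPD alters flow more on the Lung meridian than on the Heart meridian. Section 2.3 supplies only comparisons between two groups, one variable at a time. Whoever writes the conclusion must therefore set the sites side by side without a prespecified method or scale.

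The scale matters. For a positive quantity formed as a product, a proportional effect is a natural possibility. With resting PU of 1 at one site and 2 at another, a uniform 30% reduction is a drop of 0.3 at the first and 0.6 at the second. In PU the second site looks twice as affected; as a ratio both are 0.7. A reader of raw differences could report a meridian-specific effect that reflects only resting flow.

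The fallback adds a smaller difficulty. If one site is judged abnormal and another is not, one result concerns a mean difference and the other a rank comparison, and they share no effect measure. The statistician, blinded to the protocol, has only the SAP from which to take the scale.

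The moxibustion response has the same gap: the SAP does not say whether it is a change in PU or a ratio to the pre-moxibustion value.

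**Working it through.** **Inputs from the documents.** 40 COPD and 40 healthy controls (Part 2, section 2.1); significance at P < 0.05 (SAP 2.3; two-sided assumed); t test with an unnamed rank fallback (SAP 2.3). The total of 120 comes with no effect size, SD or power, so there is no sample-size figure to reproduce. For orientation, 40 against 40 detects d = (1.960 + 0.842) × √(2/40) = 0.63 with 80% power.

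**Assumptions.** PU log-normal, log-SD s = √ln(1 + CV²), CV 0.3 to 1.5; same CV at both sites; correlation 0.5 between sites on the log scale.

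**1. Raw between-site contrast under a uniform COPD ratio of 0.7.** Let one site have b times the other's resting PU, and measure in units of the lower site's healthy mean.

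- Healthy mean Lung-minus-Heart difference: b − 1. COPD: 0.7(b − 1). Group difference: 0.3(b − 1).
- Variance of the within-person difference, healthy: V = CV²(1 + b²) − 2b[√(1 + CV²) − 1]. COPD: 0.49V.
- SE = √(1.49V/40); Z = 0.3(b − 1)/SE; rejection ≈ Φ(Z − 1.96) + Φ(−Z − 1.96).

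For b = 2:

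| CV | V | SE | Z | Formula | Simulated raw | Simulated log |
|---|---|---|---|---|---|---|
| 0.3 | 0.274 | 0.101 | 2.97 | 84% | 84% | 5% |
| 0.5 | 0.778 | 0.170 | 1.76 | 42% | 42% | 5% |
| 0.7 | 1.567 | 0.242 | 1.24 | 24% | 23% | 5% |
| 1.0 | 3.343 | 0.353 | 0.85 | 14% | 13% | 5% |

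Simulations used 20,000 runs per cell. At b = 1.5 the simulated raw rates are 49%, 20%, 12% and 7%; at b = 3 they are 98%, 65%, 38% and 21%. At b = 1 the raw contrast holds 5%. The log contrast stays at about 5% throughout.

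**2. The planned per-site tests.** A t statistic is unchanged when PU is multiplied by a constant, so resting level alone cannot favour a site. At CV 0.5 and b = 2, simulated power is 0.88 at both sites. A result significant at one site only occurs in 15% of runs on raw PU and 12% on log PU; at CV 0.7, 33% and 29%. Changing scale barely improves that way of judging specificity.

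**3. The switching rule.** Read as: Shapiro-Wilk P < 0.05 in either group leads to Mann-Whitney, otherwise the raw t test. The COPD ratio is set to give the log t test about 80% power (6,000 runs for power, 3,000 for type I error).

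| CV | Log t | Raw t | Switching rule | Rank test triggered | Type I error of rule |
|---|---|---|---|---|---|
| 0.3 | 0.78 | 0.76 | 0.77 | 70% | 0.052 |
| 0.5 | 0.78 | 0.75 | 0.77 | 97% | 0.056 |
| 0.7 | 0.79 | 0.72 | 0.77 | >99% | 0.053 |
| 1.0 | 0.79 | 0.66 | 0.76 | 100% | 0.048 |
| 1.5 | 0.79 | 0.58 | 0.77 | 100% | 0.044 |

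The rule recovers most of what the raw t test loses. Two sites receive different tests in 6.5% of runs at CV 0.5 and in under 1% at CV 0.7 and 1.0.

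**The case against.** The strongest reply is that the rejection rates of 13% to 84% belong to a contrast the SAP does not contain. That is correct. A reader might infer that the planned per-site tests themselves turn a uniform effect into a site-specific one; step 2 shows they do not. What stands is that the objective calls for a between-site conclusion and the SAP gives no way to reach one, so the scale of that comparison is left open.

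Three other stronger readings are tempting and unsupported:

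- **Substantial power loss.** This is true of a raw t test kept regardless of skewness (0.66 against 0.79 at CV 1.0). The SAP moves skewed data to a rank test, and the net loss is about 1 to 2 points.
- **Inflated false positives from switching.** An analyst who ran both tests and kept the smaller P value would have an error rate of about 7% per site. SAP 2.3 ties the choice to the distribution, and a fixed normality criterion keeps the rate near 5%. The gap is only that no criterion is fixed.
- **Managers choosing the test after seeing results.** SAP 1.1 says they verify methods. It does not say they select them, or when.

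It is also fair to say that a product need not be log-normal and that nothing in the documents shows COPD effects to be proportional. If COPD lowered PU by the same 0.3 at sites resting at 1 and 2, the ratios would be 0.70 and 0.85, and the log contrast would be the misleading one. That limits confidence in the sizes, but it strengthens the case for fixing the scale beforehand, since the scale determines what site-specific means. A named rank test at every site would cure the inconsistency of tests, but would not supply a between-site estimate. Finally, the descriptive summaries in SAP 2.2 are planned whichever test is used, so effect information is not wholly absent; a formal estimate with an interval is.

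**Conclusion.** The point holds in a limited form. SAP 2.3 leaves the scale of a primary outcome, the fallback test and its trigger unspecified, and offers no analysis that answers the site-specificity objective. Were sites compared on raw PU, a uniform COPD ratio of 0.7 would be declared site-specific in about 13% to 84% of trials when one site has twice the other's resting PU (CV 1.0 down to 0.3), against about 5% on log PU. This rests on log-normal PU, equal CVs, correlation 0.5 and 40 per group; the documents supply only the group size. The harm disappears if resting PU is similar across sites.

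The missing between-site contrast matters more than the power loss. Confidence is moderate. The change is worth making because it serves a stated objective at little cost, but its importance lies between minor and should-fix.

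**What to change.** Replace the test-selection rule in SAP 2.3 with wording to this effect:

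- PU is analysed as natural-log PU at every site and in every group, whatever the observed distribution. Results are ratios of geometric means with 95% CI.
- Site specificity in COPD is tested as the group difference in within-person log(Lung PU / Heart PU), reported as a ratio of ratios with 95% CI. State how the two points on each meridian are combined, for example as the mean of their log values.
- The moxibustion response at each site is the ratio to the same session's pre-moxibustion PU.
- A named rank test (for example Mann-Whitney for two-group comparisons) is a sensitivity analysis only, applied at all sites or none.

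In SAP 1.1, state that the research managers' check of methods is completed before any group-coded data are released.

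The cost is SAP wording and a little added analysis. No extra participants or measurements are needed. Tables would show ratios beside raw PU, which readers used to PU may find less familiar.
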